 604 and be provided a 48 h carbohydrate refeeding diet on days 1 and 2 to restore muscle glycogen
 605 content pre-SUSOPS (**Figure 3**). On day 2, following an ≥ 8 h fast (0000 h), volunteers will
 606 undergo the first of three fractional iron absorption studies (Iron
 607 Study 1), during which time volunteers will ingest a stable isotopically labeled iron ($^{54}\text{FeSO}_4$)
 608 drink followed by serial blood draws over the next 6 h. A fasting blood draw and percutaneous

609 muscle biopsy of the vastus lateralis will be collected on the morning of day 3. Volunteers will
610 also complete approximately 3-4 mood/cognitive-performance familiarization sessions and 1
611 baseline session before the SUSOPS testing period. Immediately thereafter, volunteers will
612 complete a 72-h SUSOPS, and will be provided either sufficient food (combat rations) to
613 maintain energy balance within $\pm 10\%$ of estimated total daily energy expenditure (SUSOPS
614 BAL) or only enough food to match 45% of total daily energy expenditure to elicit severe
615 negative energy balance (SUSOPS NEG BAL). Volunteers will reside at the Doriot Climatic
616 Chambers during the SUSOPS beginning the evening of days 1 and 11 (volunteers will be
617 provided standardized meals), and ending after final data collection on days 6 and 16.
618 Throughout these periods, volunteers will wear the USARIEM Vigilance Monitoring System, the
619 Fatigue Science Readiband™ actigraph, Philips Respironics Actiwatch® Spectrum Plus, or
620 equivalent device on their non-dominant wrist. The activities performed will be comprised of
621 load carriage and unloaded steady-state exercise and Warfighter operational tasks (e.g., 15 m
622 timed casualty evacuation drag of a 123 kg dummy, move under fire, prepare fighting positions)
623 to increase total daily energy expenditures. Physical performance will be assessed before and
624 after each SUSOPS. Mood, cognitive performance and overall vigilance will also be assessed.
625 Sleep will be restricted to four hours per night during SUSOPS to mimic recent field studies. On
626 day 6, immediately following the final exercise bout and 8 h after dinner on day 5, a second
627 muscle biopsy will be collected (alternate leg from biopsy one) and volunteers will undergo Iron
628 Study 2 ($^{57}\text{FeSO}_4$). Days 7-12 will serve as a recovery period from SUSOPS 1 (Recovery 1).

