629 Fasted blood draws will be collected on days 7-9 during Recovery 1, and a second baseline
630 mood/cognitive test session will occur during Recovery 1. Starting on day 11, volunteers will
631 complete a second glycogen normalization and 48 h carbohydrate refeeding protocol. On day
632 13, following an overnight fast, a blood draw and a third muscle biopsy (alternate leg from
633 biopsy two) will be collected. Immediately thereafter, volunteers will complete the second 72 h
634 SUSOPS. All testing, planned activity, and sleep restrictions will be the same as described for
635 SUSOPS I; however, volunteers will switch to either SUSOPS BAL or SUSOPS NEG BAL. Iron
636 Study 3 ($^{58}\text{FeSO}_4$) and the fourth and final muscle biopsy (alternate leg from biopsy three) will
637 occur on day 16 immediately following the final exercise bout and 8 h after dinner on day 15.
638 Days 17-22 will serve as Recovery 2 (7 d post-SUSOPS recovery blood draw will be collected on
639 day 22 to match the 7 d recovery from SUSOPS 1) Diet records will be recorded on days 6-8,
640 and 16-18.

641

642 **SUSOPS BAL and SUSOPS NEG BAL**

643 The SUSOPS will be comprised of a variety of Warfighter tasks, designed to elicit high energy
644 expenditures, muscle damage and fatigue, sleep deprivation, and decrements in physical and
645 cognitive performance as well as self-reported mood status. Most importantly, the SUSOPS will
646 be designed to elicit a marked inflammatory response. Physical activity/exercise will be
647 prescribed at levels to expend ~ 5000 - 6000 total kcal/d using the ACSM metabolic equations for
648 steady-state exercise [64] and the compendium of metabolic equivalents for physical activities
649 [65]. Total daily energy expenditure estimates will be consistent with our recent reports in
650 Norwegian Soldiers and matched between SUSOPS BAL and NEG BAL [55, 66]. Combat
651 rations (Meal Ready-to-Eat) will serve as the underlying diet during SUSOPS BAL and NEG
652 BAL (refer to SUSOPS Diet Intervention section for details). Low-to-moderate intensity (30 - 65%
653 $\text{VO}_{2\text{peak}}$) steady-state endurance-type exercise will be the primary exercise modality.
654 Volunteers will perform three prolonged steady-state exercise bouts per day. All three exercise
655 sessions will be conducted outdoors on Natick Soldier Systems Center grounds (NSSC fitness
656 trail). Two of the three exercise bouts will be ~ 60 - 180 -min load carriage exercise sessions,

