744 only ~4-10 mg supplemental iron and will be consumed with one meal each day to mimic iron
745 intake during SUSOPS BAL (iron content of SUSOPS BAL is approximately 20-25 mg/d). Water
746 will be allowed ad libitum and total amount consumed will be recorded by study team members.
747 During the 48 hours prior to each SUSOPS period (beginning on days 1 and 11, volunteers will
748 be fed meals derived of commercially available foods which will meet calculated energy
749 requirements to maintain their body weight.
750

751 Volunteers will receive instructions from study dietitians on how to consume an ad libitum diet
752 with the same macronutrient distribution during the two recovery periods (see "Choosing Your
753 Foods During Recovery" document). Food records will be maintained by study volunteers on
754 days 6-8 and 16-18. Volunteers will meet with study dietitians to review these records. These
755 records will be used to determine how energy deficit during SUSOPS impacts food selection
756 during recovery. Physical activity will be restricted during both recovery periods.
757

758 **Determination of Total Daily Energy Expenditure**

759 Doubly labeled water (DLW) will be used to determine actual TDEE during SUSOPS 1 and
760 SUSOPS 2 and verify the accuracy of estimated TDEE. DLW will be administered during the first
761 iron study on day 2 (~0000 h after an 8 h fast). Immediately before drinking the DLW, volunteers
762 will provide a urine sample to determine the natural abundance of ^{18}O and ^2H . They will not eat or
763 drink anything for 4 h (~0400 h) after consuming a total of 120 g DLW containing 10% H_2^{18}O
764 (~0.285 g $\text{H}_2^{18}\text{O}\cdot\text{kg}$ total body water $[\text{TBW}]^{-1}$) and 99% $^2\text{H}_2\text{O}$ (~0.15 g $^2\text{H}_2\text{O}\cdot\text{kg}$ TBW^{-1} ; Sigma-
765 Aldrich, St. Louis, MO or similar company). The DLW dose container will be rinsed with local tap or
766 bottled water, which the volunteer will drink. Urine samples will then be collected approximately 4 h
767 and 6 h after the DLW dosing for initial TBW determinations to be made. Volunteers will be free to
768 eat and drink after these urine samples.

769
770 Two volunteers will be chosen at random to consume only locally available drinking water to control
771 for natural changes in ^2H and ^{18}O abundance (local water will be analyzed to determine isotopic

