803 precision of 1-3%. The volunteer will lay face-up on the DEXA densitometer table in shorts, t-
804 shirts, and stocking feet, and will be asked to remain motionless for the 8-10 min scan. The
805 InBody measure takes less than a minute to complete, will be performed immediately before or
806 after the DEXA, with volunteers wearing the same clothing described for DEXA. These data will
807 be used to calculate body water, protein (i.e., lean mass), mineral (i.e., bone), and fat mass.

808

809 **Determination of Peak Oxygen Uptake**

810 Peak oxygen uptake ($\dot{V}O_{2peak}$) will be determined using an indirect, open circuit respiratory
811 system (True Max 2400, ParvoMedics, Sandy, Utah, USA) on a cycle ergometer. The value will
812 be used to better estimate exercise-induced energy expenditure (EIEE) during SUSOPS and to
813 determine the workloads necessary for the glycogen normalization protocol (see below).
814 Volunteers will be clothed in appropriate athletic attire and perform this assessment in a
815 temperature and humidity controlled room. The volunteer will be allowed to warm-up by
816 pedaling at 70 W for 5 min. At the start of testing, the volunteer will put on a nose clip and a
817 mouthpiece connected to a 2-way respiratory valve, which is attached to a head piece to hold it
818 in place. Every minute, workload intensity will be progressively increased by 30 W until the
819 volunteer is fatigued or unable to maintain a pedaling rate that either maintains or increases O_2
820 consumption. Heart rate will be monitored using a heart-rate monitor (Polar Electro Inc, Oulu,
821 Finland) and recorded during the last 30 sec of each workload. The test will be stopped
822 immediately if the subject reports angina-like symptoms, exertional syncope, shows signs of
823 poor perfusion (i.e., light-headedness, confusion, ataxia, pallor, cyanosis, nausea, or cold and
824 clammy skin), or if the testing equipment fails.

825

826 **Glycogen Normalization Protocol**

827 To normalize muscle glycogen content and its potential influence on inflammation leading into
828 both SUSOPS periods [days 1 and 11 following an overnight fast (≥ 10 h)], participants will
829 perform a glycogen normalization protocol followed by a 2-d refeeding protocol. The glycogen
830 normalization protocol will be completed on a cycle ergometer. The intensity will be based on

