831 $\dot{V}O_{2peak}$. Volunteers will begin with a 5 min warm-up at 50% $\dot{V}O_{2peak}$ before beginning the
832 protocol. After a warm-up period, the cycle ergometer protocol is comprised of repeated periods
833 of 2 min of work at $80 \pm 5\% \dot{V}O_{2peak}$ followed by 2 min of recovery at $50 \pm 5\% \dot{V}O_{2peak}$. The
834 protocol will last approximately 50-min (12 work:rest cycles). To ensure familiarity with the
835 testing procedures, volunteers will perform one practice session during the baseline pre-study
836 period. Volunteers will be permitted to consume water *ad libitum* during the protocol.

837

838 After completing the glycogen depletion protocol, volunteers will be fed a controlled diet
839 prescribed to maintain energy balance and provide at least 6.0 g carbohydrate $\cdot kg^{-1} \cdot d^{-1}$ (~55-
840 60% of total energy consumed) to ensure adequate glycogen repletion and homogeneous
841 glycogen levels within and across volunteers between SUSOPS phases (BAL and NEG BAL).
842 All food and beverages (except water) will be prepared and provided by study dietitians and
843 consist largely of military combat ration and supplemental food items.

844

845 **Determination of Fractional Iron Absorption**

846 Volunteers will undergo three acute fractional iron absorption studies (Iron Studies 1, 2, and 3).
847 The studies will occur on days 2, 6, and 16 in the morning (~0000 h) after an 8 h fast. The iron
848 studies on days 6 and 16 will occur ~3 h after completing the last exercise bout of the SUSOPS
849 to correspond to peak hepcidin responses to exercise. An indwelling 18 gauge intravenous
850 catheter will be placed in the antecubital fossa (or distally) and a baseline blood sample will be
851 drawn before consuming the iron isotope (0 min). Volunteers will then consume a 300 mL drink
852 containing 3.8 mg iron (representative of dietary iron in an iron-rich meal) as isotopically labeled
853 $^{54}FeSO_4$, $^{57}FeSO_4$, or $^{58}FeSO_4$ (Trace Sciences International). Venous blood samples will be
854 collected at 20, 40, 60, 120, 240, and 360 min-post iron loading [70] to assess the effects of a
855 transient exercise-induced increase in IL-6 (and hepcidin) on the appearance of absorbed iron
856 in blood.

857

858 **Percutaneous Muscle Biopsy of the Vastus Lateralis**

859 Percutaneous muscle biopsies will be obtained from the vastus lateralis using a 5 mm

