1144 Fasted (≥ 8 h) blood draws, and post-exercise blood draws will be collected as outlined below to
1145 assess fractional iron absorption and relevant biomarkers of inflammation, muscle damage,
1146 appetite, and nutritional and metabolic stress responses to SUSOPS (**Tables 1**). A total of 42
1147 blood draws (≤ ~530 mL) will be collected during the entire study.

1148

1149 **Table 1.** Blood sample collection per analyte¹

	SUSOPS 1					Recovery 1				SUSOPS 2				Recovery 2			
Days	2	3	4	5	6	7	8	9	12	13	14	15	16	17	18	19	22
Tracer/tracee ²	7	x	x	x	7	x	x	x	x	x	x	x	7	x	x	x	x
Hgb/Hct	x	x	x	x	x	x	x	x	x	x	x	x	x	x	x	x	x
Erythroferrone ²	7	x	x	x	7	x	x	x	x	x	x	x	7	x	x	x	x
c-myomiRNA		x		x	x					x		x	x				
Exo miRNA		x		x	x					x		x	x				

Ferritin ²	7	x	x	x	7	x	x	x	x	x	x	x	7	x	x	x	x
sTfR	x	x	x	x	x	x	x	x	x	x	x	x	x	x	x	x	x
Hepcidin ²	7	x	x	x	7	x	x	x	x	x	x	x	7	x	x	x	x
Iron ²	7	x	x	x	7	x	x	x	x	x	x	x	7	x	x	x	x
TIBC	x	x	x	x	x	x	x	x	x	x	x	x	x	x	x	x	x
IL-6 ²	7	x	x	x	7	x	x	x	x	x	x	x	7	x	x	x	x
hs-CRP	x	x	x	x	x	x	x	x	x	x	x	x	x	x	x	x	x
Erythropoietin		x			x					x			x				
Cortisol		x		x		x		x	x	x		x		x		x	x
CK		x		x		x		x	x	x		x		x		x	x
LDH		x		x		x		x	x	x		x		x		x	x
Myoglobin		x		x		x		x	x	x		x		x		x	x
T-test		x		x		x		x	x	x		x		x		x	x
SHBG		x		x		x		x	x	x		x		x		x	x
LH		x		x		x		x	x	x		x		x		x	x
DHEA-S		x		x		x		x	x	x		x		x		x	x
Insulin ³		2		2		x		x	x	2		2		x		x	x
FFA ³		2		2		x		x	x	2		2		x		x	x
Glycerol ³		2		2		x		x	x	2		2		x		x	x
Glucose ³		2		2		x		x	x	2		2		x		x	x
β-HB ³		2		2		x		x	x	2		2		x		x	x
Osmolality	x	x	x	x	x	x	x	x	x	x	x	x	x	x	x	x	x
Leptin ³		x		x		x		x		x		x		x		x	
Acyl ghrelin ³		2		2		x		x		2		2		x		x	
PYY ³		2		2		x		x		2		2		x		x	
GLP-1 ³		2		2		x		x		2		2		x		x	
PP ³		2		2		x		x		2		2		x		x	
I-FABP ³		2		2						2		2					
Zonulin ³		2		2				x		2		2				x	
LBP ³		2		2				x		2		2				x	
S100B ³		2		2				x		2		2				x	
Ex vivo PBMC	x				x								x				
Serum archive ⁴	8	2	x	2	8	x	x	x	x	2	x	2	8	x		x	x
EDTA archive ⁴	x	2	x	2	x	x	x	x	x	2	x	2	x	x		x	x
LiHep archive ⁴	x	2	x	2	x	x	x	x	x	2	x	2	x	x		x	x
mRNA-seq	x				x			x					x			x	
Metabolomics	x				x			x					x			x	

1150 ¹Analyte abbreviations: Hbg/Hct, hemoglobin/hematocrit; c-myoMIR, circulating muscle-specific
1151 microRNA; sTfR, soluble transferrin receptor; T-saturation, transferrin saturation; TIBC, total iron binding
1152 capacity; IL-6, interleukin-6; hs-CRP, high-sensitivity C-reactive protein; CK, creatine kinase; LDH, lactate

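### The day 12 and day 22 late-recovery draws match on elapsed time but not on conditions: day 12 follows the day 11 glycogen ride and falls within refeeding, day 22 follows neither

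*Combined protocol and SAP*

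**What the plan says.** All references are to the combined protocol and SAP.

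- **Recovery 1** (B5.3, Experimental Design): "Days 7-12 will serve as a recovery period from SUSOPS 1 (Recovery 1". Recovery 2 is days 17-22, with a late draw on "day 22 to match the 7 d recovery from SUSOPS 1". The sentence does not name the matching day.
- **Draws** (B5.4, Table 1, "Blood sample collection per analyte"): days 7, 8, 9 and 12 in Recovery 1; days 17, 18, 19 and 22 in Recovery 2. IL-6 and hepcidin are drawn on all of these. CK, myoglobin, cortisol, insulin, FFA and glucose are drawn on days 7, 9, 12, 17, 19 and 22.
- **Ride and refeeding** (B5.3, Experimental Design): "Starting on day 11, volunteers will" "complete a second glycogen normalization and 48 h carbohydrate refeeding protocol". The Glycogen Normalization Protocol section schedules the ride ahead of "both SUSOPS periods [days 1 and 11 following an overnight fast" and describes its size: the "protocol will last approximately 50-min (12 work:rest cycles", with work bouts at about 80% of VO2peak. A controlled diet with at least 6.0 g/kg/d of carbohydrate follows. No ride is scheduled before day 22.
- **Recovery otherwise** (B5.3, Diet and Total Daily Energy Expenditure Prescription): diet is ad libitum under dietitian instruction. The paragraph ends "during recovery. Physical activity will be restricted during both recovery periods".
- **Analysis** (B5.8.2, Primary Objectives): mixed models with phase (diet), time within phase and their interaction. Group and group-by-phase enter initial models as a carryover check and are removed if they add nothing significant to the fit. Post hoc comparisons are Bonferroni-corrected paired t-tests.

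**The concern.** In a crossover, the BAL versus NEG BAL comparison at a given recovery day is clean only if that day is handled alike in both periods apart from diet. The late day is not. Every man does the ride and starts refeeding on day 11, so his period 1 late sample is taken a day after hard intervals and on a prescribed diet. His period 2 late sample is taken after several days of rest and free eating. Half the diet contrast at that time point, roughly, compares a post-ride sample under one diet with a rested sample under the other, and the other half the reverse.

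The protocol has its own reason to care: it standardises glycogen before each SUSOPS because glycogen may influence inflammation, and B2 describes IL-6 as exercise-driven. At stake is the late-recovery level of the inflammatory, muscle-damage and metabolic markers, and any statement that they have or have not settled after each diet.

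**Working it through.** **1. Timing.** SUSOPS 1 ends on day 6 and SUSOPS 2 on day 16. 12 − 6 = 6 and 22 − 16 = 6, so the plan's match on elapsed time reproduces. It is 7 days only if days 6 and 16 are counted. If day 13 were meant instead (13 − 6 = 7), that draw also follows the ride and refeeding, so the mismatch in conditions remains.

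**2. Conditions side by side.**

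| | Day 12 | Day 22 |
|---|---|---|
| Days since SUSOPS ended | 6 | 6 |
| Glycogen ride the day before | yes | no |
| Diet | controlled, high carbohydrate | ad libitum |
| Residence | chambers since the evening of day 11 | not in the scheduled residence |

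**3. What the model can absorb.** Let d be the shift in a marker at day 12 caused by ride and refeeding. It occurs in period 1, at one time point. In a two-period, two-diet crossover, group-by-phase is the period effect. As specified it is constant over time within phase, so even if retained it cannot represent a shift at one time. That needs a period-by-time term (group-by-phase-by-time), which the plan does not name. The paired t-tests have no period term at all.

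**4. Effect on the diet contrast.** Take each man's late-recovery difference, NEG BAL minus BAL. Men with NEG BAL first (n1) carry +d and men with BAL first (n2) carry −d.

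- Bias = d(n1 − n2)/(n1 + n2). For 8/7 this is d/15 = 0.07d; for 9/6, 0.20d; for 10/5, 0.33d. The documents do not state the allocation ratio.
- SD of the difference is about √(SD² + d²) near balance. With R = d/SD, the standardised effect is divided by √(1 + R²).

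**5. Power.** As a check on the plan's figures in B5.8.1, a two-sided paired t-test (noncentral t, alpha 0.05) with the first hepcidin row, 4.7/4.9 = 0.959, gives 82% at n = 11; the second, 7/7.4 = 0.946, gives 81%. The stated n of 11 reproduces. At n = 15, 4.7/4.9 gives 93%.

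The size of d is not in the documents, so R is an assumed range. The standardised effect giving 80% power at n = 15 (the figure stated in B5.2.2) is 0.778.

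| Assumed R | 0.778/√(1 + R²) | Power, n = 15 | Power, n = 15, starting from 4.7/4.9 |
|---|---|---|---|
| 0 | 0.778 | 80% | 93% |
| 0.25 | 0.755 | 78% | 92% |
| 0.5 | 0.696 | 71% | 87% |
| 1.0 | 0.550 | 51% | 69% |

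**The case against.** The case for leaving this alone is substantial, and much of it stands.

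- **The match is one of time.** The sentence promises a match to a recovery day, not to conditions, and elapsed time does match. That day 12 is the counterpart is inferred from Table 1, and Figure 3 is not shown. A reader might infer that the draws are mistimed because the recovery periods span 6 days. Counting from days 6 and 16, when the post-SUSOPS food records also start, gives 7. This is wording, with no analytic effect.
- **Activity restriction.** A reader might infer a contradiction with the day 11 ride. The restriction can fairly be read as covering the volunteers' own activity rather than a scheduled study procedure. The text should be made explicit; it is not an independent flaw.
- **No hypothesis rests on this contrast.** The primary objectives concern the 72 h SUSOPS. Iron absorption is measured on days 2, 6 and 16, jump tests end on day 19, and leptin, ghrelin and PYY are not drawn on days 12 or 22. No return-to-baseline test is named. This stands as a limit on importance. Days 12 and 22 can nevertheless enter as levels of time within phase, and then into the post hoc tests.
- **A large offset is unlikely for the main markers.** B2 describes muscle-derived IL-6 as falling quickly after exercise and ties the sustained rise to tissue injury, with eccentric work as the example. B5.3 times the iron studies to a hepcidin peak about 3 h after exercise. So 1.0 SD a day after cycling has no support for IL-6 or hepcidin. That argument does not address insulin, FFA or glucose under a different diet.

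What the objection does not answer is that the conditions differ and the specified analysis cannot account for it.

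**Conclusion.** The concern holds for one time point. Days 12 and 22 are equally distant from SUSOPS but differ in recent exercise and diet, so late-recovery levels are not comparable between periods, and the specified model cannot separate that difference from diet.

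Three stronger conclusions are not supported. First, the mismatch does not in itself favour either diet: with an 8/7 split only 1/15 of the offset remains as bias, and the rest appears as variance. This relies on near-balanced sequences among men with data, which the plan does not guarantee. Second, it does not touch the SUSOPS-day contrasts or the day 6 and 16 iron contrasts. Third, the fall to 71% or 51% is not an expected loss. It depends on an assumed offset and on a late-recovery test that the study was not sized for; at 0.25 SD the fall is only to 78%, and starting from the plan's first hepcidin row every figure is higher.

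It is worth correcting because it is real, confined and cheap to remove.

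**What to change.** 1. In B5.8.2, state that days 12 and 22 are not analysed as matched recovery levels of time within phase. Base recovery contrasts on days 7-9 versus 17-19, or days 7 and 9 versus 17 and 19 for analytes drawn only then.
2. Use days 3 and 13 as the matched pre-SUSOPS samples; both follow ride and refeeding. Pairing day 12 with day 2 is not a substitute: day 2 carries the iron study and doubly labelled water, and has no CK, cortisol or insulin draw.
3. If a late recovery point is wanted, move the two existing draws to the fasted morning of day 11, before the ride, and to day 21. Both are 5 days after SUSOPS ends (11 − 6 = 21 − 16 = 5).
4. If days 12 and 22 are kept, include period and period-by-time terms without a significance test for removal, and take model-based contrasts in place of plain paired t-tests.
5. Reconcile the statements on the 7-day recovery, the day 7-12 and 17-22 windows, and activity restriction.

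Cost: items 1, 2 and 5 are wording. Item 3 adds no draws but brings the late point forward by one day. Item 4 spends a few degrees of freedom in a small sample.

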684 marker and assume the predetermined position for that marker. This will be repeated until they
685 have covered a total of 100 m (15 rushes of ~6.6 m). After starting in the prone position, the
686 next two positions will be kneeling, and then a prone position until the course is completed.
687 Time to complete the task will be recorded. Each testing session will take approximately 1-2
688 minutes.

689

690 *Casualty Evacuation Drag:* Volunteers will drag a simulated casualty (approximately 123 kg) up
691 to 15 m as fast as possible in 60 sec, while wearing an approximately 32 kg fighting load
692 [comprised of the basic uniform (~5.3 kg), weapon and tactical equipment (~11.2 kg), and
693 rucksack (~15 kg)]. If the volunteer is unable to pull the casualty the full 15 m in 60 sec, the
694 distance the casualty was dragged will be measured to the nearest 0.25 m.

695

696 *Prepare Fighting Positions (Sandbag Carry):* While wearing a fighting load minus the weapon
697 (approximately 26.5 kg), volunteers will lift and carry a total of 16 sandbags weighing 18 kg
698 each, carry them 10 m, and place them on the floor in a 4 bag wide x 2 bag deep x 2 bag high
699 formation as quickly as possible. The completion time will be recorded. The test is expected to
700 take approximately 3-5 minutes per volunteer.

701

702 **Diet and Total Daily Energy Expenditure Prescription during SUSOPS**

703 Volunteers will complete a 3 d diet record and a 3 d activity log during baseline pre-study testing
704 (days -14-0) and according to instructions provided by a registered dietitian to characterize pre-
705 study diet and exercise habits (see "Diet Record" and "Activity Log"). To predict total daily
706 energy expenditure (TDEE), volunteers' resting metabolic rate (RMR) will be measured during
707 the baseline pre-study testing period using standardized techniques and an indirect, open circuit
708 respiratory system (True Max 2400, ParvoMedics, Sandy, Utah, USA). RMR will be multiplied

709 by a factor of 1.3 to estimate energy expenditures for activities of daily living. Together, these
710 data will serve as the baseline total daily energy requirements for SUSOPS 1 and 2.
711

712 To increase TDEE to approximately 5000-6000 kcal/d, volunteers will be prescribed low-to-
713 moderate intensity (30-65% of pre-determined peak oxygen uptake, VO_{2peak} and corresponding
714 heart rate) endurance-type exercise using the ACSM metabolic equations for steady-state

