715 exercise [64] and the compendium of metabolic equivalents for physical activities (refer to
716 descriptions of Determination of Peak Oxygen Consumption and SUSOPS BAL and SUSOPS
717 NEG BAL below) [65].
718

719 For example, an 85 kg individual with a baseline total daily energy requirement (RMR of 2000
720 kcal/d * 1.3) of 2600 kcal/d and a VO_{2peak} of 45 mL/kg/min, would expend approximately 2468
721 kcal during two, 90-min load carriage exercise bouts combined [i.e., 85kg+32kg load = 117 kg *
722 (~50% of VO_{2peak} is 6.7 METS *3.5 mL/kg/min)/1000] * (90 min of work * 5 kcal/L/min) = 1234
723 kcal/exercise bout], 600 kcal during a 60-min unloaded exercise session (calculations follow the
724 same format), and approximately 100 kcal/d performing the Warfighter tasks, for an estimated
725 TDEE of ~5768 kcal/d. TDEE prescriptions are individualized to each volunteer's requirements
726 and will be held constant between SUSOPS 1 and 2. Exercise intensities, total duration
727 exercised, and TDEE will likely differ between volunteers. Every attempt will be made to
728 maintain TDEE between 5000-6000 kcal/d across all volunteers; however, some individuals
729 may expend more and others less.
730

731 Registered Dietitians will develop individualized daily menus for SUSOPS 1 and 2 using Food
732 Processor SQL (ESHA Research, Salem, OR, Version 10.14). The diets during each SUSOPS
733 period will be derived primarily from components of the US military Meals Ready-to-Eat (MRE)
734 rations to achieve appropriate macronutrient proportions. The macronutrient distribution of the
735 MRE-based diets will not be manipulated. Thus, volunteers will be consuming a diet providing
736 approximately 60% carbohydrate, 10-15% protein, and 25-30% fat. The macronutrient
737 distribution, as a % of total energy, will remain constant during SUSOPS NEG BAL by uniformly
738 reducing total energy intake across carbohydrate, protein, and fat. This feeding paradigm will
739 most closely resemble field-feeding practices observed during recent USARIEM studies [55,
740 66]. The micronutrient content of the ration will not be altered. However, to limit the potential
741 confounding effect of differing iron intakes across SUSOPS 1 and 2, volunteers will consume
742 supplemental iron sulfate mixed in water (Ferrous sulfate drops, RxChoice, available OTC)
743 during SUSOPS NEG BAL to match total iron consumed during SUSOPS BAL. This equates to

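### The worked TDEE estimate counts resting energy during exercise twice, so it is about 6% (at most about 8%) above a once-counted total, and each diet's absolute energy balance is mislabelled

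*Combined protocol and SAP*

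**What the plan says.** The calculation is in B5.3, under Diet and Total Daily Energy Expenditure Prescription during SUSOPS.

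- **Baseline.** Measured RMR is multiplied "by a factor of 1.3 to estimate energy expenditures for activities of daily living. Together, these" "data will serve as the baseline total daily energy requirements for SUSOPS 1 and 2". The baseline is thus a whole-day figure.
- **Example, baseline term.** "For example, an 85 kg individual with a baseline total daily energy requirement (RMR of 2000" "kcal/d * 1.3) of 2600 kcal/d and a VO_{2peak} of 45 mL/kg/min, would expend approximately 2468" is how the example opens; 2468 is the kcal cost of the two loaded bouts.
- **Example, exercise term.** The loaded bouts are costed on body mass plus load: "kcal during two, 90-min load carriage exercise bouts combined [i.e., 85kg+32kg load = 117 kg", multiplied by a rate and duration given as "50% of VO_{2peak} is 6.7 METS *3.5 mL/kg/min)/1000] * (90 min of work * 5 kcal/L/min) = 1234" kcal per bout. A 60-min unloaded session adds 600 kcal by the same method, and the Warfighter tasks add about 100 kcal.
- **Total.** The example concludes: "TDEE of ~5768 kcal/d. TDEE prescriptions are individualized to each" volunteer. The prescription is then kept the same for both SUSOPS periods.
- **Use.** Under Experimental Design in B5.3, BAL is food within 10% of estimated TDEE, and the alternative is "BAL) or only enough food to match 45% of total daily energy expenditure to elicit severe" negative balance.
- **Checks.** DLW is used to verify the estimate, and fasted body weight is taken daily. Neither section gives a rule for changing intake in response.

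**The concern.** A whole-day baseline already charges every hour with at least resting energy. The example sets its exercise rate at about half of VO2peak, and VO2peak is measured as total oxygen uptake (B5.3, Determination of Peak Oxygen Uptake). The exercise rate is therefore also a total that includes rest. Adding the two without removing the overlap charges rest twice for every hour of prescribed exercise.

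This matters because the estimate is more than descriptive: it sets the food in both conditions. If it runs high, the condition labelled energy balance leans towards surplus, the deficit condition is milder than its label, and a tolerance meant to be symmetric is partly used up before feeding starts. The plan states no step that would correct this while a volunteer is being fed.

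**Working it through.** **Inputs**, all from the worked example in B5.3: RMR 2000 kcal/d; factor 1.3; body mass 85 kg; load 32 kg; 6.7 METs; 3.5 mL/kg/min per MET; 5 kcal per L of oxygen; two 90-min loaded bouts; one 60-min unloaded bout; 100 kcal/d for tasks.

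**1. Reproduce the plan's figure.**
- Baseline: 2000 × 1.3 = 2600 kcal/d.
- Loaded bout: 117 × 6.7 × 3.5 / 1000 × 90 × 5 = 1234.6 kcal; two bouts, 2469 (stated 2468).
- Unloaded bout: 85 × 6.7 × 3.5 / 1000 × 60 × 5 = 598 kcal (stated 600).
- Sum of the stated terms: 2600 + 2468 + 600 + 100 = 5768 kcal/d, exactly as stated. The full 2600 is used.

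**2. Confirm that the exercise rate includes rest.** 6.7 × 3.5 = 23.45 mL/kg/min, which is 52% of the VO2peak of 45. That matches the example's approximate 50% of a total uptake. No resting MET is subtracted.

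**3. Size of the overlap.** Exercise time is 2 × 90 + 60 = 240 min = 4 h. The time spent on the tasks is ignored.

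| What is counted twice | kcal/d | Once-counted TDEE | Excess of 5768 |
|---|---|---|---|
| Resting energy only: 2000/24 × 4 | 333 | 5435 | 333/5435 = 6.1% |
| Full baseline rate: 2600/24 × 4 | 433 | 5335 | 433/5335 = 8.1% |

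The second row additionally assumes that daily-living energy is spread evenly over all 24 h.

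**4. Effect on the diets.**

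| | As labelled | Rest counted once | Upper case |
|---|---|---|---|
| Nominal BAL, 5768 kcal | 100% | 106% | 108% |
| BAL band, 5191–6345 kcal | 90–110% | 96–117% | 97–119% |
| NEG BAL, 0.45 × 5768 = 2596 kcal | 45% | 47.8% | 48.7% |
| NEG BAL deficit, kcal/d | 3172 | 5435 − 2596 = 2839 | 5335 − 2596 = 2739 |

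**5. Dependence on bout length.** B5.3 (SUSOPS BAL and SUSOPS NEG BAL) allows loaded bouts of roughly 60 to 180 min. I assume a 60-min unloaded bout (3 to 7 h/d in all), RMR 2000 and an estimated TDEE of 5000–6000 kcal/d. For resting energy only, the excess runs from 250/(6000 − 250) = 4.3% to 583/(5000 − 583) = 13.2%. Under the even-spread assumption, the top of the range is 758/(5000 − 758) = 17.9%.

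**6. What does not change.** Both diets are fixed fractions of the same estimate. The gap between them stays at 0.55 × 5768 = 3172 kcal/d, and their ratio stays at 100:45.

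**The case against.** A reader might infer two stronger conclusions. The documents support neither.

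*That BAL is fed 6–8% above actual need.* The percentages are the effect of one term with the others held as written. The 1.3 factor is itself rough for men sleeping 4 h a night. If those 4 h are charged at RMR and the 4 exercise hours are left out, 2600 kcal over the other 16 h is (2600 − 333)/16 = 142 kcal/h, or 1.7 × RMR. Nothing in the plan shows that to be too much. How the carried load is costed is a separate question and could also move the total. Actual need is measured only by DLW. This objection stands, so the finding concerns the estimate, not need.

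*That the trial no longer tests energy balance against severe deficit.* A common proportional shift in a crossover favours neither condition. Nominal BAL at 106–108% is still within 10% of the once-counted TDEE. NEG BAL is still a deficit of 51–52%, close to the roughly 50% of the field study described in B2. The named contrast survives.

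The upper figure is also open to challenge. Suppose 1.3 describes a day with 8 h of sleep at RMR. Waking hours then cost (1.3 × 24 − 8)/16 = 1.45 × RMR. With 4 h of sleep and 16 h of other waking time, the non-exercise energy is 83.3 × (4 + 1.45 × 16) = 2267 kcal, and the correction is 2600 − 2267 = 333 kcal. That is the 6% figure again, which is why I lead with it.

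Two further points have partial force. The summation appears only in an example, and the cited sources for the exercise equations are not available here; still, the text around the example gives the same baseline and exercise components, and no other way of combining them is stated. Daily weighing and DLW are real checks, but neither is tied to a change in intake, and the timing of DLW results is not given.

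**Conclusion.** The addition is correct, but the terms overlap. In the worked example, resting energy for 4 h/d of exercise is counted twice: about 333 kcal/d, which puts 5768 kcal/d about 6% above the once-counted 5435. The figure reaches 433 kcal/d (about 8%) only if daily-living energy is spread evenly over 24 h. These sizes belong to this example, with all other terms as written, and vary with bout length.

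The consequence is mislabelling of each diet's absolute energy balance. Nominal BAL is about 106% (up to 108%) of the once-counted TDEE, with a tolerance band that lies mostly on the surplus side, and NEG BAL is about 48% (up to 49%). The ratio between diets, the gap of 3172 kcal/d and the within-man comparison are intact. The point deserves correction because it affects how both conditions are described, but it does not threaten the trial's main comparison.

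**What to change.** The sponsor should reconcile the baseline and exercise terms in the TDEE prescription section of B5.3 so that no hour's resting energy is counted twice, and state whether the exercise costs are gross or net of rest. The choice of formula is the sponsor's. The worked example and each volunteer's estimated TDEE should then be recomputed before menus are written. The sponsor should also check that the stated BAL tolerance and NEG BAL deficit describe what the reconciled estimate delivers.

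The cost is one line of calculation and a revised example. The stated TDEE falls slightly, so some men may sit nearer the lower end of the 5000–6000 kcal/d target.
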